### **5.6.**

### **5.7. Protocol Deviations**

Should a protocol deviation occur, the Sponsor must be informed as soon as possible. Protocol deviations and/or violations and the reasons they occurred will be included in the clinical study report. The Sponsor, or its authorized designee, will report protocol deviations to the institutional review board/independent ethics committee and in accordance with applicable regulatory authority.

This document is confidential.

## **6. General Aspects for Statistical Analysis**

### **6.1. General Methods**

- The statistical evaluation will be performed using SAS® software version 9.4 or higher (SAS Institute, Cary, NC). All data will be listed, and summary tables will be provided.
- Summary statistics will be presented by treatment group and overall. For continuous variables, data will be summarized with the number of subjects (N), mean, standard deviation (SD), median, minimum, and maximum by treatment group. For categorical variables, data will be tabulated with the number and proportion of subjects for each category by treatment group.
- The dictionary (MedDRA and WHODrug) version used will be specified in corresponding data display footnote.
- Unless otherwise stated, all listings will include all subjects in ITT Population, and all listings will be sorted by subject ID, treatment, and assessment date/time.
- For all percentage calculations, the denominator will be the number of subjects in the relevant population, unless otherwise stated.
- Only data from protocol scheduled visits will be included in the summary tables. Data from unscheduled visits will not be included in the summary tables but will be included in the listings.

### **6.2. Key Definitions**

- Baseline Value: unless otherwise defined, the last non-missing assessment prior to first dosing will serve as baseline value.

Unknown, Not Done, Not Applicable and other classifications of missing data will not be considered when calculating baseline observations. However, valid categorical observations will be considered for baseline calculations.

- Study day: number of days since the study drug administration. Study day is calculated using the formula: Study day = date of assessment - date of first dosing

### **6.3. Missing Data**

Missing data will not be estimated and/or imputed in any way. Adverse events(AEs) with missing onset dates will be included as treatment-emergent.

### **6.4. Visit Windows**

Please refer to section 3.8. Study Procedures and Flowchart for visit windows.

This document is confidential.

## 7. Demographic, Other Baseline Characteristics and Medication

### 7.1. Subject Disposition and Withdrawals

Subject disposition will be summarized and listed.

The number and percentage of subjects in each population, completed and discontinued the study, together with the reasons for discontinuation (unacceptable toxicity or AE, subject withdrawal of consent, intercurrent illness, general or specific changes in the subject's condition, subject fails to adhere to the protocol requirements, lost to follow-up, pregnancy, study terminated, other) will be presented.

### 7.2. Demographic and Other Baseline Characteristics

Demographic data and baseline characteristics will be summarized and listed for ITT Population.

Demographic data including age (years), sex (male, female), child bearing potential (yes, no), race (asian, black or african American, white, American Indian or Alaska Native, Native Hawaiian or Other Pacific Islander, other), ethnicity (Hispanic or Latino, Asian, Russian, Mixed Ethnicity, Not Reported, Unknown, Other) collected at study Screening will be summarized descriptively. Likewise, baseline characteristics including weight (kg) will also be summarized.

Age = (inform consent date - date of birth + 1) / 365.25 and truncated to complete years.

Weight (in kg) = weight (in lbs) \* 0.4536

### 7.3. Medical History and Concomitant Diseases

Medical history and concomitant illnesses will be recorded at Screening [REDACTED]. Medical history and concomitant illnesses will be coded with Medical Dictionary for Regulatory Activities (MedDRA) dictionary and summarized by system organ class (SOC) and preferred term (PT) based on the ITT Population. Medical history will also include alcohol consumption and smoking history, if applicable.

Medical history will be summarized by SOC and PT for ITT Population.

Subject listing of medical history, alcohol consumption and smoking history will be provided.

### 7.4. Other Baseline Characteristics

Other baseline characteristics including pregnancy test will be listed only.

### 7.5. Medication

Prior and concomitant medications will be coded using the World Health Organization Drug Dictionary (WHODrug). Prior and concomitant medications will be listed for ITT Population with the classification (prior and/or concomitant) identified.

#### 7.5.1. Prior Medication

All medications stopped before first dosing will be considered as prior medications.

Prior medications will be summarized by Anatomical Therapeutic Chemical (ATC) and PT for ITT Population and will be displayed in data listing.

#### 7.5.2. Concomitant Medication

All medications stopped on or after first dosing will be considered as concomitant medications. Medications with missing stop date will be considered as concomitant medication.

Concomitant medications will be summarized by ATC and PT for ITT Population. Subjects who take the same medication (in terms of the PT) more than once will only be counted once for that medication.

Subject listing of concomitant medications will be provided.

This document is confidential.

7.5.3.      **Other Therapies**

Surgical procedures will be captured in CRF.

Listing of surgical procedures will be provided.

This document is confidential.

## **8. Efficacy**

Efficacy analyses will be conducted for the ITT population, evaluable population PP population and safety population. All statistical tests for secondary efficacy endpoints will be two-sided with  $\alpha = 0.05$ .

### **8.1. Primary Efficacy Endpoint and Analysis**

There will be no primary efficacy endpoint or analysis carried out for this study.

### **8.2. Secondary Efficacy Endpoint(s) and Analyses**

#### **8.2.1. Occurrence of Recurrent Stroke**

The frequency and proportion of subjects who have a recurrent stroke [REDACTED] will be reported by treatment group and overall. [REDACTED]  
[REDACTED].

#### **8.2.2.**

[REDACTED]  
[REDACTED]  
[REDACTED]  
[REDACTED]  
[REDACTED]  
[REDACTED]  
[REDACTED]  
[REDACTED]  
[REDACTED]  
[REDACTED]

#### **8.2.3. National Institute of Health Stroke Scale**

The NIHSS is a standardized method to measure the level of impairment caused by a stroke and was developed by the National Institutes of Health. The NIHSS allows for objective comparison of efficacy across different treatments for stroke, including rehabilitation interventions.

The NIHSS is a brief and reliable stroke deficit assessment scale composed of 11 components and the numbers of grades for each component vary; however, for each component, a score of 0 is defined as normal while higher scores indicate increasing severity of impairment. The total score ranges from 0 (no deficit) to 42 (dead).

[REDACTED]  
[REDACTED]

The total score and absolute change from baseline will be summarized [REDACTED]. Data missing on the visit level will not be imputed, and no statistical inferences will be performed.

The proportion of subjects with NIHSS of 0-2 points will be presented by treatment group [REDACTED]

[REDACTED]  
[REDACTED]

This document is confidential.

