APPENDIX 2.

Institute of Health Stroke Scale (Sample)

Patient Identification: _____

Pt. Date of Birth _____/_____/_____

Hospital _____/_____/_____

Date of Exam _____/_____/_____

Interval: Baseline 2 hours post treatment 24 hours post onset of symptoms ±20 minutes 7-10 days
 3 months Other _____ (____)

Time: _____ ()am ()pm

Person Administering Scale _____

Administer stroke scale items in the order listed. Record performance in each category after each subscale exam. Do not go back and change scores. Follow directions provided for each exam technique. Scores should reflect what the patient does, not what the clinician thinks the patient can do. The clinician should record answers while administering the exam and work quickly. Except where indicated, the patient should not be coached (i.e., repeated requests to patient to make a special effort).

Instructions	Scale Definition	Score
1a. Level of Consciousness: The investigator must choose a response if a full evaluation is prevented by such obstacles as an endotracheal tube, language barrier, orotracheal trauma/bandages. A 3 is scored only if the patient makes no movement (other than reflexive posturing) in response to noxious stimulation.	0 = Alert; keenly responsive. 1 = Not alert; but arousable by minor stimulation to obey, answer, or respond. 2 = Not alert; requires repeated stimulation to attend, or is obtunded and requires strong or painful stimulation to make movements (not stereotyped). 3 = Responds only with reflex motor or autonomic effects or totally unresponsive, flaccid, and areflexic.	_____
1b. LOC Questions: The patient is asked the month and his/her age. The answer must be correct - there is no partial credit for being close. Aphasic and stuporous patients who do not comprehend the questions will score 2. Patients unable to speak because of endotracheal intubation, orotracheal trauma, severe dysarthria from any cause, language barrier, or any other problem not secondary to aphasia are given a 1. It is important that only the initial answer be graded and that the examiner not "help" the patient with verbal or non-verbal cues.	0 = Answers both questions correctly. 1 = Answers one question correctly. 2 = Answers neither question correctly.	_____

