
7. Limb Ataxia: This item is aimed at finding evidence of a unilateral cerebellar lesion. Test with eyes open. In case of visual defect, ensure testing is done in intact visual field. The finger-nose-finger and heel-shin tests are performed on both sides, and ataxia is scored only if present out of proportion to weakness. Ataxia is absent in the patient who cannot understand or is paralyzed. Only in the case of amputation or joint fusion, the examiner should record the score as untestable (UN), and clearly write the explanation for this choice. In case of blindness, test by having the patient touch nose from extended arm position.
 
8. Sensory: Sensation or grimace to pinprick when tested, or withdrawal from noxious stimulus in the obtunded or aphasic patient. Only sensory loss attributed to stroke is scored as abnormal and the examiner should test as many body areas (arms [not hands], legs, trunk, face) as needed to accurately check for hemisensory loss. A score of 2, "severe or total sensory loss," should only be given when a severe or total loss of sensation can be clearly demonstrated. Stuporous and aphasic patients will, therefore, probably score 1 or 0. The patient with brainstem stroke who has bilateral loss of sensation is scored 2. If the patient does not respond and is quadriplegic, score 2. Patients in a coma (item 1a=3) are automatically given a 2 on this item.
 
9. Best Language: A great deal of information about comprehension will be obtained during the preceding sections of the examination. For this scale item, the patient is asked to describe what is happening in the attached picture, to name the items on the attached naming sheet, and to read from the attached list of sentences. Comprehension is judged from responses here, as well as to all of the commands in the preceding general neurological exam. If visual loss interferes with the tests, ask the patient to identify objects placed in the hand, repeat, and produce speech. The intubated patient should be asked to write. The patient in a coma (item 1a=3) will automatically score 3 on this item. The examiner must choose a score for the patient with stupor or limited cooperation, but a score of 3 should be used only if the patient is mute and follows no one-step commands.
 
10. Dysarthria: If patient is thought to be normal, an adequate sample of speech must be obtained by asking patient to read or repeat words from the attached list. If the patient has severe aphasia, the clarity of articulation of spontaneous speech can be rated. Only if the patient is intubated or has other physical barriers to producing speech, the examiner should record the score as untestable (UN), and clearly write an explanation for this choice. Do not tell the patient why he or she is being tested.
	
0 = Absent:
 
1 = Present in one limb:
 
2 = Present in two limbs:
 
UN = Amputation or joint fusion; explain: _____

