**10.14. Proportion of Subjects With NIHSS Change from Baseline**

The proportion of subjects with an increase in the NIHSS of  $\geq 4$  points, increase of 1-3 points, no increase/decrease, decrease of 1-3 points and decrease  $\geq 4$  points from Baseline [REDACTED]

[REDACTED]. [REDACTED]

[REDACTED] No formal adjustment for multiple comparisons will be made. [REDACTED]

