#### **14.2.5.2. Table Conventions**

- Units will be included where available
- If the categories of a parameter are ordered, then all categories between the maximum and minimum category are presented in the table, even if n=0 for all treatment groups in a given category that is between the minimum and maximum level for that parameter. For example, the frequency distribution for symptom severity would appear as:

Severity Rating	N
severe	0
moderate	8
mild	3

Where percentages are presented in these tables, zero percentages will not be presented and so counts of 0 will be presented as 0 and not as 0 (0%).

- If the categories are not ordered (e.g., Medical History, Reasons for Discontinuation from the Study, etc.), then only those categories for which there is at least 1 subject represented in 1 or more groups are included.
- An Unknown or Missing category are added to each parameter for which information is not available for 1 or more subjects.
- Unless otherwise specified, the estimated mean and median for a set of values are printed out to 1 more significant digit than the original values, and SDs are printed out to 2 more significant digits than the original values. The minimum and maximum should report the same significant digits as the original values. For example, for systolic blood pressure:

N	XX
Mean	XXX.X
Std Dev	X.XX
Median	XXX.X
Minimum	XXX
Maximum	XXX

- P-values are output in the format: "0.xxx", where xxx is the value rounded to 3 decimal places. Every p-value less than 0.001 will be presented as <0.001. If the p-value are less than 0.0001, then present as <0.0001. If the p-value is returned as >0.999, then present as >0.999
- Percentage values are printed to one decimal place, in parentheses with no spaces, one space after the count (e.g., 7 (12.8%), 13 (5.4%)). Pre-determine how to display values that round down to 0.0. A common convention is to display as '<0.1', or as appropriate with additional decimal places. Unless otherwise noted, for all percentages, the number of subjects in the analysis set for

This document is confidential.

the treatment group who have an observation will be the denominator. Percentages after zero counts should not be displayed and percentages equating to 100% are presented as 100%, without decimal places.

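### NIHSS 42 is labelled as death without a visible rule for scoring deaths, and SAP 6.1 and 14.2.5.2 give contradictory denominators for the NIHSS rates

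*SAP*

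**What the plan says.** Protocol 11.1 and SAP 8.2.3 describe the NIHSS range in the same terms: "The total score ranges from 0 (no deficit) to 42 (dead". The instrument itself is in Protocol Appendix 2. Its worst level of consciousness is "3 = Responds only with reflex motor or autonomic effects or totally unresponsive, flaccid, and areflexic", which describes an unresponsive patient. Its ataxia item adds "Ataxia is absent in the patient who cannot understand or is paralyzed".

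SAP 8.2.3 summarises total score and change from baseline, and gives the proportion of each arm scoring 0-2. SAP 10.14, in the safety chapter, tabulates categories of change: a rise of 4 or more at one end, then "increase of 1-3 points, no increase/decrease, decrease of 1-3 points", then a fall of 4 or more.

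On missing data, SAP 6.3 says "Missing data will not be estimated and/or imputed in any way". SAP 8.2.3 repeats this for the NIHSS: "Data missing on the visit level will not be imputed, and no statistical inferences will be performed".

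On denominators there are two general defaults. SAP 6.1 says "the denominator will be the number of subjects in the relevant population, unless otherwise stated". SAP 14.2.5.2 says that the analysis-set subjects in "the treatment group who have an observation will be the denominator". The visible text of 8.2.3 and 10.14 names no denominator of its own. By contrast, the mRS text in 8.2.4 codes death as 6 and names the denominator of its shift tables, and the two hemorrhage sections, 10.10 and 10.11, name theirs.

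Lines directly after the range statement in 8.2.3, after the 0-2 sentence, and after the change categories in 10.14 are redacted.

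**The concern.** Calling 42 *dead* gives that score a meaning that the appended instrument does not have. A programmer with only the visible text could enter 42 at each visit after a death. The same programmer could equally treat those visits as missing and leave them unfilled. The two readings give different tables.

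The denominator conflict adds to this. Under one default, an unscored subject stays in the NIHSS 0-2 denominator and counts as not achieving it; under the other, the subject leaves the calculation.

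The direction of the error matters in a trial whose primary objective is safety. If deaths are left missing, an arm with more deaths can show less neurological worsening and, under one of the two defaults, a better 0-2 rate. If deaths are scored 42, the rates behave properly, but one assigned value can dominate the mean change of a small arm without being marked as assigned.

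**Working it through.** **1. The stated range.** Item maxima from Appendix 2, in order (1a, 1b, 1c, gaze, visual, face, left and right arm, left and right leg, ataxia, sensory, language, dysarthria, inattention):

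3 + 2 + 2 + 2 + 3 + 3 + 4 + 4 + 4 + 4 + 2 + 2 + 3 + 2 + 2 = 42.

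The plan's figure of 42 is reproduced. With ataxia scored absent, as item 7 directs for a patient who is paralyzed or cannot understand, the ceiling is 42 − 2 = 40. No item has a level for death, so 42 can stand for death only by assignment.

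**2. Arm sizes.** SAP 3.5 gives about 24 subjects randomized 2:1: 24 × 2/3 = 16 on LT3001 and 24 × 1/3 = 8 on placebo. The documents give no expected death rate, so each step below takes one death in an arm.

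**3. Death left missing: worsening by 4 or more (SAP 10.14).** Assume the death is the arm's only worsening event.

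| Arm | Death counted | Missing, population denominator (6.1) | Missing, observed denominator (14.2.5.2) |
|---|---|---|---|
| n = 8 | 1/8 = 12.5% | 0/8 = 0% | 0/7 = 0% |
| n = 16 | 1/16 = 6.3% | 0/16 = 0% | 0/15 = 0% |

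The event leaves the numerator under either rule.

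**4. Death left missing: NIHSS 0-2 (SAP 8.2.3).** Assume half the arm reaches 0-2.

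| Arm | Population denominator (6.1) | Observed denominator (14.2.5.2) |
|---|---|---|
| n = 8 | 4/8 = 50% | 4/7 = 57.1% |
| n = 16 | 8/16 = 50% | 8/15 = 53.3% |

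The rate rises only under 14.2.5.2.

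**5. Death scored 42.** Entry NIHSS is 4 to 30 (SAP 3.4.1); assume baseline lies in the same range. The change is then 42 − 30 = +12 to 42 − 4 = +38. Both exceed 4, so the death counts as worsening, and 42 is not within 0-2. The two rates are therefore sensible.

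For mean change, let b be the baseline of the subject who died and m the mean change of the other n − 1 subjects. Scoring the death 42 instead of omitting it shifts the arm mean by (42 − b − m)/n.

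| m (assumed) | b | n = 8 | n = 16 |
|---|---|---|---|
| 0 | 30 | 12/8 = 1.50 | 12/16 = 0.75 |
| 0 | 4 | 38/8 = 4.75 | 38/16 = 2.38 |
| −4 | 30 | 16/8 = 2.00 | 16/16 = 1.00 |
| −4 | 4 | 42/8 = 5.25 | 42/16 = 2.63 |

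**The case against.** The case for leaving the plan alone has real substance.

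- **42 is on the scale.** A reader might infer that the plan uses a score the instrument cannot produce. Step 1 of the working shows otherwise: 42 is the sum of the item maxima. Only its meaning as death is absent, and the 40-point ceiling for a comatose patient changes no analysis.
- **The label and the ban on imputation need not conflict.** If death is assigned 42, as the mRS assigns 6, the score is not missing and the no-imputation rule does not apply. This stands. The fault is that the visible text does not say which reading applies.
- **Redaction.** A reader might infer that the plan has no rule for deaths. The documents do not support that: a rule may sit in the redacted lines of 8.2.3 or 10.14. The table index is not shown, the shells are a separate document, and 14.2.5.2 sends denominator details to footnotes or programming notes.
- **Deaths do not simply vanish.** Under 6.1 they stay in the 0-2 denominator. SAP 14.2.5.2 adds an Unknown or Missing category where information is lacking, and 14.2.4 separates the analysis-set size from the number observed. Deaths are also tabulated in 10.12 and 10.13 and appear as mRS 6. This stands and limits the harm, but it does not put the event back in the worsening row.
- **The summaries are descriptive.** Score and change carry no inference, and the median, minimum and maximum accompany the mean. This also stands.
- **Mean change among survivors is not an obvious remedy.** It omits deaths from the mean, which is the very effect at issue. The choice is debatable, and the fix does not depend on it.

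None of this removes the mislabelled score or reconciles the two denominators, both of which are in unredacted text.

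**Conclusion.** The point holds in limited form. Two defects are visible whatever the redactions contain: both documents attach death to a score for which the appended instrument has no such level, and SAP 6.1 and 14.2.5.2 contradict each other on the default denominator. Whether deaths are scored or left missing is open only as far as the visible text goes.

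The consequence depends on the reading. Left missing, one death costs the 10.14 worsening row up to 12.5 percentage points in an arm of 8 or 6.3 in an arm of 16, under either denominator. The 0-2 rate is inflated only under 14.2.5.2, by about 7 points (n=8) or 3 points (n=16) in the example. Scored 42, the distortion is confined to mean change: 1.5 to 4.75 points (n=8) or 0.75 to 2.4 (n=16) if the others average 0.

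These sizes rest on one death per arm, a response rate of one half, baselines of 4 to 30, and no other worsening in the arm. The documents supply only the baseline range and the arm sizes. The overall impact is modest, but the correction is worth making because one of the affected tables is a safety table.

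**What to change.** 1. Make SAP 6.1 and 14.2.5.2 state the same denominator for the NIHSS rates: the analysis population.
2. In SAP 8.2.3, count subjects who died as not achieving NIHSS 0-2.
3. In SAP 10.14, show subjects who died either in the row for a rise of 4 or more or in a separate row for deaths.
4. In Protocol 11.1 and SAP 8.2.3, remove the label *dead* or state how it is used, so that an assigned 42 does not enter mean change unmarked. Show the number of deaths per arm beside the mean and median change.
5. If a redacted rule, footnote or table shell already covers deaths, confirm that it agrees with these statements.

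The cost is a few lines of SAP wording, one protocol phrase and some table footnotes. No new data are needed. The rates will look slightly less favourable in an arm with deaths.
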